8.5.1 Primary efficacy analysis

The 11-point NRS value for a specific week will be determined by the worst NRS score collected on the daily NRS questionnaire for the seven days prior (day – 7 to day -1) to the week 8 visit (or planned visit date if week 8 visit not performed). If the daily NRS questionnaire is not completed for 7 consecutive days prior to the week 8 visit, the worst NRS score between the eCRF (Item: What is the highest NRS score over the past 7 days according to the patient?) and the NRS questionnaire completed by the patient will be used. The change in patient-reported pericarditis pain using an 11-point NRS from baseline to 8 weeks will be presented as a continuous variable.

8.5.2 Additional efficacy analysis

- The change in patient-reported pericarditis pain using an 11-point NRS from baseline to 26 weeks will be summarized as a continuous variable.
- The change in patient-reported pericarditis pain using an 11-point NRS from baseline to other intermediate weeks (i.e. visits 3,4,5,6,7) will be summarized as a continuous variable.
- Patients with normalized CRP levels (i.e with a CRP \leq 0.5 mg/dL) at 8 weeks (for patients with CRP \geq 1.0 mg/dL at baseline) will be summarized as a categorical variable
- Patients with normalized CRP levels (i.e with a CRP \leq 0.5 mg/dL) at 26 weeks (for patients with CRP \geq 1.0 mg/dL at baseline) will be summarized as a categorical variable
- Patients with pericarditis recurrence during the extension period (EP), i.e with an adverse event occurring between week 8 and week 26 and coded with the following LLT code 10087207 (Recurrent pericarditis) will be summarized as a categorical variable

- Time to CRP normalization (in days) (i.e time between IMP start date up to the first blood draw date when $CRP \leq 0.5 \text{ mg/dL}$) for patients with $CRP \geq 1.0 \text{ mg/dL}$ at baseline will be summarized as a continuous variable. If CRP had not normalized at the timepoint assessed (i.e 8 week visit date (for SSA) or 26 weeks visit date for the final analysis), the patients concerned will not be included in the analysis for this outcome.
- CRP change from baseline at 26 weeks (%) will be summarized as a continuous variable.

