### 6.2 *Extension Period*

Unless contraindicated in the opinion of the investigator, after 8 weeks of study treatment, patients will enter an 18-week extension period (EP) in which they continue study treatment while their concomitant medications to treat pericarditis will be weaned, as described in Section 6.6.

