### 6.3 *Follow-up Procedures*

At every assessment before study drug dose increase the patient will be re-evaluated. This includes ECG monitoring at approximately 5 hours post-morning dose ( $T_{max}$ ) to surveil for deleterious effects on ECG intervals (particularly the QTc interval) and rhythm.

Drug titration will be dependent on investigator or designate interrogation of the ECGs and the absence of abnormalities on those ECGs.

Vital signs, blood chemistry including liver function tests, hematology as well as INR assessments will be carried out at selected visits. Concurrent medications and (S)AEs will be recorded at all visits.

Final efficacy assessments will take place after 26 weeks of study treatment and include a clinical assessment, vital signs, Pain score NRS, a 12-lead ECG, the C-SSRS, as well as laboratory assessments.

For patients who do not enter the EP, final assessments will be done after 8 weeks, i.e. at Visit 5.

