## **6.7 Management of Pericarditis Recurrence During the Extension Period**

Pericarditis recurrence during the extension period is defined as the recurrence of typical pericarditis pain associated with supportive objective evidence of pericarditis in the opinion of the investigator. At any timepoint during the EP, patients who experience suspected recurrence of their pericarditis will have been instructed to inform their site Investigator as soon as possible. Patients who experience a suspected recurrence of pericarditis symptoms will be requested to report to the study site/clinic for a scheduled or unscheduled visit, during which clinical assessments will be performed to gather all the necessary diagnostic data to confirm or rule out the presence of pericarditis recurrence. The Investigator will evaluate all assessments performed for a diagnostic workup, whether at the study site or at locations outside.

Following communication with the study medical monitor, patients who report at least 1 day with pericarditis pain measurement  $\geq 4$  on the 11-point NRS **AND** have a CRP value  $\geq 1$  mg/dL (either on the same day or separated by no more than 7 days) during the EP of the trial will receive rescue therapy at the discretion of the investigator, i.e., if not already taking; analgesics first, then NSAIDs, and then colchicine. Immunosuppressive therapy such as corticosteroids or rilonacept may be added for pericarditis recurrence at the discretion of the investigator.

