### **9.2.11    Management of AEs**

#### ***9.2.11.1   AE Reporting***

An AE is defined as any new untoward medical occurrence or worsening of a pre-existing medical condition in a patient or clinical investigation patient administered an investigational (medicinal) product and that does not necessarily have a causal relationship with this treatment. An AE can therefore be any unfavorable and unintended sign (including an abnormal laboratory finding, for example), symptom, or disease temporally associated with the use of investigational product, whether or not considered related to the investigational product.

AEs can be spontaneously reported or elicited during open-ended questioning, examination, or evaluation of a patient. (In order to prevent reporting bias, patients should not be questioned regarding the specific occurrence of one or more AEs.)

Any AE that results in any of the following outcomes will be considered an SAE:

1. Death

2. Life-threatening situation (patient was at risk of death at the time of the event. This does not refer to an event that might have caused death if it was of greater intensity.)
3. New in-patient hospitalization or prolongation of existing index hospitalization
4. Persistent or significant disability or incapacity
5. Congenital anomaly or birth defect
6. QTc interval increases to > 500 msec or >60 msec from baseline.
7. Important medical events that may not result in death, be life-threatening, or require hospitalization but may jeopardize the patient and may require medical or surgical intervention to prevent one of the above outcomes (based upon appropriate medical judgment), e.g., allergic bronchospasm requiring intensive treatment in an emergency room or at home, blood dyscrasias or convulsions that do not result in in-patient hospitalization, or the development of drug dependency or drug abuse. Potential Drug-Induced Liver Injury (DILI) is also considered an important medical event. (See Section 9.2.11.3 for the definition of potential DILI.)

All SAEs experienced by a patient after informed consent has been obtained must be reported to SOCAR Research (SOCAR) within 24 hours of the site's awareness of the event.

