**4 Study drug adjustment up to Visit 4 (Week 3); drug accountability at all visits, including virtual visits**

 Adverse Event recording starts after informed consent is obtained

 All local laboratory assessments at baseline to be performed before start of study Rx

 Pregnancy test in women with childbearing potential

 For patients not able to participate in the EP, Visit 5 (Week 8) is the end of study visit  
 EP starting after Visit 5 until Visit 9

 If CRP was measured within 3 days

If CRP was measured within 7 days of Day 1, this value will be used as the baseline value. If there is no CRP measurement available within 7 days of Day 1, CRP needs to be measured at baseline.

Highest NRS pain score within the past 7 days of Day 1 from patient recall; after randomization from the Patient Portal entries/diary entries or, if not available, from patient recall

 Visits 2 (Day 3), 3 (Day 10), and 4 (Week 3) can be performed virtually, via video link, if an ECG can be performed with direct transmission to site for review by investigator or designate and local laboratory assessments at Visit 4 can be arranged

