8.6.1 Adverse events (AEs)

The number of adverse events and percentage of patients with at least one adverse event will be summarized by system organ class and by preferred terms (MedDRA).

AEs will be considered as treatment - emergent adverse events (TEAE) if the event onset time (and date) is $>$ start of the IMP. Adverse events with incomplete onset dates will be summarized as TEAE regardless of severity and relationship to the IMP.

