9.3 Precision

The precision of original measurements will be maintained in summaries. Where possible, means, medians and standard deviations will be presented with an increased level of precision; means and medians will be presented to one more decimal place than the raw data, and the standard deviations will be presented to two more decimal places than the raw data.

Percentages will be based on available data and denominators will exclude missing values. For frequency counts of categorical variables, categories where counts are zero will be displayed for the sake of completeness. For example, if none of the patients discontinue due to "lost to follow-up," this reason will be included in the table with a count 0. Categories with zero counts will not have zero percentages displayed.

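### SAP 8.5.2 counts extension-period recurrence by matching one MedDRA term that is not tied to the protocol 6.7 definition, and no denominator is named for the percentage

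*SAP*

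**What the plan says.** Protocol 6.7 defines recurrence in the EP as "recurrence of typical pericarditis pain associated with supportive objective evidence of pericarditis in the opinion of the investigator". A patient with a suspected recurrence is seen at a scheduled or unscheduled visit, and a diagnostic work-up establishes whether one is present. The pain and CRP thresholds later in 6.7 govern rescue therapy; they are not part of the definition.

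SAP 8.5.2 turns the endpoint into a coding rule. A patient has a recurrence if they are "with an adverse event occurring between week 8 and week 26 and coded with the following LLT code 10087207 (Recurrent pericarditis"). It does not cite protocol 6.7.

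On who can have the event, protocol 6.2 says: "Unless contraindicated in the opinion of the investigator, after 8 weeks of study treatment, patients will enter an 18-week extension period (EP"). Protocol 6.3 adds: "For patients who do not enter the EP, final assessments will be done after 8 weeks, i.e. at Visit 5". Protocol 17.2, footnote 9, bounds the period: "EP starting after Visit 5 until Visit 9". The endpoint is listed as a percentage of patients, and Table 21 is where it is reported. SAP 9.3 gives the only general rule: "Percentages will be based on available data and denominators will exclude missing values". SAP 2.3.3 states that the data needed for this outcome exist for every enrolled patient.

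**The concern.** The SAP rule and the protocol definition are different tests, and no step shows that they pick out the same patients. Every participant already has recurrent pericarditis (inclusion criterion 2), and an AE includes "any new untoward medical occurrence or worsening of a pre-existing medical condition". A site could therefore describe the same confirmed event in several ways, while a match on one lowest-level term depends on how the reported wording is coded. In the other direction, an AE with that code counts whether or not objective evidence was found.

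The percentage also lacks a stated base. Two programmers could use different ones and both comply with the SAP.

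What is at stake is modest but relevant. Protocol 3.5 gives the feasibility of weaning background therapy during the EP as one purpose of the pilot, with the results informing a randomized withdrawal trial. Recurrence during the EP is the listed endpoint closest to that purpose.

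**Working it through.** The plan gives no recurrence rate, precision or formal sample size for this endpoint, so there is no figure to reproduce. The check compares the texts and then sizes the effect.

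**Numerator: the two tests side by side**

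| Situation | Protocol 6.7 | SAP 8.5.2 |
|---|---|---|
| Confirmed recurrence, AE coded to LLT 10087207 | counted | counted |
| Confirmed recurrence, AE coded to another pericarditis term | counted | missed |
| AE coded to LLT 10087207, no objective evidence | not counted | counted |

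No passage requires a confirmed recurrence to carry that code, or an AE with that code to meet 6.7.

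**Would another planned output reveal a mismatch?** SAP 8.6.1 says the "percentage of patients with at least one adverse event will be summarized by system organ class and by preferred terms (MedDRA"). Tables 25 to 28 follow that layout. A recurrence coded to a different pericarditis preferred term would appear in Table 26 or 28 and could prompt a question. One coded to a different lowest-level term under the same preferred term would not stand out. The tables are not described as split by study period. Listing 4 (medications) could show rescue therapy, and Listing 5 (AEs) has no specified columns. SAP 6 plans a second data review meeting before lock but lists no reconciliation of recurrences. So hints exist, but no planned reconciliation.

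**Time window.** SAP 8.5.2 uses nominal weeks, while protocol 17.2 uses visits. Visit 5 may fall 4 days and Visit 9 may fall 5 days either side of nominal, so events near the edges could be placed differently.

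**Denominator.** SAP 8.5.2 names none. The Table 21 title as extracted names none either, but it ends in a comma, so text may be lost. Tables 18 and 19 do name their base. SAP 8.6 assigns an analysis set to safety; SAP 8.5 assigns none to efficacy. The Full Analysis Set (FAS) in SAP 5.1 is everyone enrolled who started study drug, which includes patients who never enter the EP. Under SAP 9.3 it is unclear whether such a patient is missing or recurrence-free.

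**Size.** Inputs:
- about 25 patients (protocol 11.1), with the FAS taken as 25 (assumption);
- EP entrants taken as 20, 24 or 25 (assumption; not in the documents);
- recurrence counts chosen for illustration.

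One misclassified patient moves the rate by 100/n points:
- n = 25: 100/25 = 4.0
- n = 24: 100/24 = 4.2
- n = 20: 100/20 = 5.0

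Counting non-entrants as recurrence-free multiplies the rate by entrants/FAS (20/25 = 0.80, 24/25 = 0.96, 25/25 = 1.00):

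| Entrants | Recurrences | Over entrants | Over FAS of 25 | Difference (points) |
|---|---|---|---|---|
| 20 | 2 | 10% | 8% | 2 |
| 20 | 5 | 25% | 20% | 5 |
| 20 | 8 | 40% | 32% | 8 |
| 24 | 6 | 25% | 24% | 1 |
| 25 | any | same | same | 0 |

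**The case against.** The strongest reply is that the SAP rule is simply the operational form of 6.7. The protocol leaves the judgement to the investigator, the investigator reports the AE, and the chosen term names the endpoint. Validation detail is deferred to a Data Management Plan that is not available here (protocol 13.2.2), and erroneous or incomplete data are queried in-house (13.3.2). EP entry is the default, and the endpoint's wording makes EP patients the natural base. SAP 2.3.3 can be read as being about which amendment a patient enrolled under, not about EP entry. SAP 9.1 reports counts with percentages, so a reader who knows the number of entrants can recompute. The endpoint is additional and descriptive, in an uncontrolled pilot. Sampling uncertainty is far larger than the shifts above: the exact 95% interval for 5/20 is 8.7% to 49.1%.

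Most of this stands, and it limits the weight of the point. A reader might infer that the SAP rule under-reports recurrence, or that the planned outputs could never expose a mismatch. The documents support neither: no wrong count is shown, errors could go either way, and the preferred-term tables and Listing 4 could give a signal.

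Two things remain. The written rule differs from the written definition, and no visible step reconciles them. And however SAP 2.3.3 was meant, it does not fit follow-up that ends at Visit 5 for non-entrants.

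**Conclusion.** The point holds as a minor one. The SAP's event rule is not the protocol's definition, the link between them is unstated and unchecked, and the base of the percentage is open. The number and net direction of any misclassifications cannot be derived from the documents. If one occurs, it is worth 4.0 points over 25 patients and 5.0 over an assumed 20 entrants. In the assumed cases, the denominator choice is worth 0 to 8 points, and nothing if every patient enters the EP. It would go too far to say that the base is beyond reasonable inference: EP entrants are the sensible choice, and the SAP only needs to say so. The reservation about the Table 21 title does not affect 8.5.2 itself, which names no base.

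**What to change.** In SAP 8.5.2:
- Define the event as a recurrence that meets protocol 6.7 in the investigator's opinion, with onset after Visit 5 until Visit 9.
- Identify candidates from AEs under any pericarditis-related term and from rescue-therapy entries in the concomitant-medication records.
- List the candidates at the second data review meeting, before lock. Send unclear cases to the investigator, whose opinion decides; the meeting does not adjudicate.
- Keep the LLT 10087207 match as a cross-check and list any discrepancies.

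For Table 21, use FAS patients who entered the EP as the denominator and say so in the title. Report beside it the number who did not enter and the number who left the EP early without a recurrence, so that incomplete follow-up is visible. Correct SAP 2.3.3 to match.

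The cost is some SAP wording, one item at a meeting already planned, and possibly a few site queries. Protocol 9.2.11.1 already asks sites to keep AE-related assessments, laboratory tests, ECGs and imaging in the source notes, which should help them answer. The change introduces no clinical rule and leaves the protocol definition untouched.

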#### 4.1.3 Additional Efficacy Parameters of Interest

- Pain score using 11-point NRS from baseline (highest pain score within the past 7 days of Day 1) to Week 26 (highest pain score during the past 7 days of Week 26)
- Percentage of patients with normalized CRP levels at 8 weeks (for patients with CRP  $\geq 1.0$  mg/dL at baseline)
- Percentage of patients with pericarditis recurrence during the EP
- Percentage of patients with normalized CRP levels at 26 weeks (for patients with CRP  $\geq 1.0$  mg/dL at baseline)
- Time to CRP normalization for patients with CRP  $\geq 1.0$  mg/dL at baseline
- CRP change from baseline at 26 weeks (%)

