The laboratory test results, vital signs and ECG data for visit 4 (week 2) protocol amendment 1 and visit 4 (week 3), protocol amendment 2 will be combined and labelled as Week 2-3.

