7 STAGED STATISTICAL ANALYSIS (SSA)

As mentioned in section 1, the analyses for this trial will be done in a staged manner – i.e. the first analysis will be performed for data collected up to the week 8 visit and the second analysis will be done when the last patient last visit is performed and the database is declared ready for complete database lock. The following data will be presented in the SSA:

- Baseline data for all patients enrolled:
 - Patient demographics: age, gender, race, ethnicity
 - Past medical history: N (%) of patients by previous episodes of pericarditis category (i.e., 2, 3, 4, or >4);
 - N (%) of patients for whom medications at baseline were prescribed for pain and pericarditis: analgesics, opiates, NSAIDs, colchicine and corticosteroids. The medications concerned will be identified as those with following

Anatomical Therapeutic Chemical (ATC) classification: H02 (Corticosteroids for systemic use), M01 (anti-inflammatory and antirheumatic products), M04 (antigout preparations), N02A (Opioids), N02B (other analgesics and antipyretics)

- N (%) of patients prescribed medications for pain and pericarditis i.e. medications which were started up to and including the Week 8 visit date and for which the stop date was either empty or > enrolment date at the time of enrolment
- CRP value at baseline will be summarized as a continuous variable
- NRS scores at baseline will be summarized as a continuous variable
- Primary efficacy endpoint, i.e. the change in patient-reported pericarditis pain using an 11-point NRS from baseline to 8 weeks – see section 8.5.1.
- Additional efficacy endpoints (see section 8.5.2):
 - Patients with normalized CRP levels (i.e. with a CRP \leq 0.5 mg/dL) at 8 weeks (for patients with CRP \geq 1.0 mg/dL at baseline) will be summarized as a categorical variable.
 - Time to CRP normalization (in days – see section 8.5.2) up to the Week 8 visit date for patients with CRP \geq 1.0 mg/dL at baseline will be summarized as a continuous variable. If CRP had not normalized at the timepoint assessed in the analysis (e.g. week 8), the patients concerned was not included in the analysis - Time to CRP normalization
 - CRP change from baseline at 8 weeks will be summarized as a continuous variable.
- Study drug exposure:
 - N (%) of patients with highest tolerated dose of (up to Week 8 visit date):
 - 10mg/kg of body weight b.i.d.
 - 7.5mg/kg of body weight b.i.d.
 - 5.0mg/kg of body weight b.i.d.

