8.5.3 Further exploratory analyses

- Evaluate the NRS for patients with qualifying $CRP \geq 1.0 \text{ mg/dL}$
- Evaluate the NRS for patients who qualified for the trial on basis of past CMR findings and had qualifying $CRP < 1.0 \text{ mg/dL}$
- Examine the correlation between medications used to treat pericarditis and the NRS score at different time points.
- Perform a numerical comparison with the historical data from the rilonacept phase 2 and RHAPSODY trials for the patients with similar eligibility criteria. The methodology to do this analysis will be addressed in a separate SAP.

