9 GENERAL PRINCIPLES

9.1 Standard descriptive statistics

The analyses will be presented/reported using summary tables, figures, and data listings. Continuous variables will be summarized with counts, means, standard deviations, medians, Interquartile range, minimums, and maximums.

Categorical variables will be summarized by counts and by percentage of patients.

All analyses and tabulations will be performed using SAS Version 9.3 or higher on a PC platform. Table, listings, and figures will be presented in RTF or Microsoft Word format. Upon completion, primary endpoints results will be validated by an independent programmer. In addition, all program output will undergo a senior level statistical review.

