10 TABLES, FIGURES AND LISTINGS

10.1 List of tables

Table 1 – Protocol deviations summary overview

Table 2 – Demographics

Table 3 – Pericarditis History

Table 4 – Cardiovascular History

Table 5 – Other medical history by MedDRA System Organ Class

Table 6 – Other medical history by MedDRA Preferred Term

Table 7 – Baseline medication by WHO Anatomical Therapeutic Chemical (ATC) Classification

Table 8 – Anthropometric assessment and vital signs at baseline – Descriptive statistics

Table 9 – Physical examination at baseline – Descriptive statistics

Table 10 –Questionnaire at baseline: NRS and C-SSRS – Descriptive statistics

Table 11 – Standard 12-lead Electrocardiogram (ECG) at baseline – Descriptive statistics

Table 12 –Laboratory tests results at baseline – Descriptive statistics

Table 13 –Laboratory tests results at baseline – Descriptive statistics by gender

Table 14 –Laboratory tests results at baseline below, within and above the normal range

Table 15 – Study drug exposure

Primary efficacy endpoint

Table 16 – Primary endpoint – Worst 11-point NRS score at Week 8 and 11-point NRS change from baseline to Week 8 – Descriptive statistics

Additional efficacy endpoints

Table 17 – Worst 11-point NRS score and change from baseline by week up to 26 weeks – Descriptive statistics

Table 18 – Patients with normalized CRP levels (i.e with a CRP \leq 0.5 mg/dL) at 8 weeks and 26 weeks (for patients with CRP \geq 1.0 mg/dL at baseline)

Table 19 – Time to CRP normalization (in weeks) for patients with CRP \geq 1.0 mg/dL at baseline

Table 20 – CRP change from baseline at 26 weeks – Descriptive statistics

Table 21 – Patients with pericarditis recurrence during the extension period (EP),

Further exploratory endpoints

Table 22 – Worst 11-point NRS score and change from baseline by week up to 26 weeks for patients enrolled with qualifying CRP ≥ 1.0 mg/dL – Descriptive statistics

Table 23 – Worst 11-point NRS score and change from baseline by week up to 26 weeks for patients for patients who qualified for the trial on basis of past CMR findings and had qualifying CRP < 1.0 mg/dL – Descriptive statistics

Safety related

Table 24 – Overview of reported adverse events

Table 25 – Non-serious adverse events by MedDRA System Organ Class

Table 26 – Non-serious adverse events by MedDRA Preferred Term

Table 27 – Serious adverse events by MedDRA System Organ Class

Table 28 – Serious adverse events by MedDRA Preferred Term

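### Time to CRP normalization leaves out every patient who did not normalize, so Table 19 reports a time conditional on success rather than the speed of normalization in the CRP ≥1.0 mg/dL group

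*SAP*

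**What the plan says.** Protocol 4.1.3 lists the endpoint as "Time to CRP normalization for patients with CRP" ≥1.0 mg/dL at baseline, without restricting it to patients who reach normal levels. SAP 8.5.2 defines it as the "time between IMP start date up to the first blood draw date when" CRP is ≤0.5 mg/dL and treats it as a continuous variable. For patients who have not normalized at the Week 8 visit (staged analysis) or the Week 26 visit (final analysis), it says that "the patients concerned will not be included in the analysis for this outcome". SAP 7 repeats the rule for the staged analysis: "the patients concerned was not included in the analysis".

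The summary that follows is the general one in SAP 9.1: "Continuous variables will be summarized with counts, means, standard deviations, medians, Interquartile range, minimums, and maximums". No Kaplan-Meier, cumulative-incidence or other censored-data summary appears in the SAP text or in its lists of tables and figures. SAP 8.5.2 gives the time in days, whereas the title of Table 19 begins "Time to CRP normalization (in weeks" and names the whole CRP ≥1.0 mg/dL group.

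After baseline, CRP is scheduled at Weeks 3, 8, 16 and 26 (SAP Table 4-1). The Week 2 visit under Amendment 1 and the Week 3 visit under Amendment 2 "will be combined and labelled as Week 2-3".

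**The concern.** A patient whose CRP is still raised at the last draw has a normalization time known only to exceed that draw. Deleting such patients selects the analysis set on the outcome. What remains is the average time among those who succeeded by the cutoff. That average is bounded by the cutoff however slow the group is, and it need not change when the share of successes changes.

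The title of Table 19 describes the full baseline CRP ≥1.0 mg/dL group, so a reader who quotes the time without Table 18 would attribute it to that group. The protocol (3.5) says the pilot is to inform a later randomized withdrawal trial, so a descriptive figure of this kind may be reused. SAP 8.5.3 also plans to "Perform a numerical comparison with the historical data from the rilonacept phase 2 and RHAPSODY trials". Whether this time enters that comparison is not stated. If it does, a normalizers-only figure would not be comparable with one estimated in all patients.

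**Working it through.** **Inputs.** The documents give no expected normalization rate, no expected time, and no number of patients with CRP ≥1.0 mg/dL (a patient may qualify on CMR instead). There is therefore no stated figure to reproduce. Planned CRP draws after baseline are taken as days 21, 56, 112 and 182. Response rates and time patterns below are assumptions.

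**1. Poor versus good response.** Let a share *p* normalize by cutoff *T*, with P(normalized by *t*) = 1 − (1 − p)^((t/T)^k). Here k = 1 is a constant rate, k = 0.5 a falling rate and k = 2 a rising rate. Each event is assigned to the next planned draw.

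Example, k = 1, T = 56:
- p = 0.10: by day 21, 1 − 0.9^0.375 = 0.0387, leaving 0.0613 for day 56. Planned mean = (0.0387×21 + 0.0613×56)/0.10 = 42.4 days.
- p = 0.70: by day 21, 1 − 0.3^0.375 = 0.3633, leaving 0.3367. Planned mean = (0.3633×21 + 0.3367×56)/0.70 = 37.8 days.

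| Cutoff, pattern | Normalizers-only mean, 10% → 70% | Whole-group median, 10% → 70% |
|---|---|---|
| Week 8, constant | 42.4 → 37.8 | not reached → 56 |
| Week 8, falling | 34.1 → 29.9 | not reached → 21 |
| Week 8, rising | 50.9 → 48.2 | not reached → 56 |
| Week 26, constant | 116.0 → 98.4 | not reached → 112 |
| Week 26, falling | 82.4 → 65.1 | not reached → 112 |
| Week 26, rising | 148.6 → 136.0 | not reached → 182 |

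The normalizers-only median at Week 8 goes from 56 to 21, 21 to 21 and 56 to 56 days in the three patterns. Drawing 6 of 25 patients at day 14, as under Amendment 1, gives 43.1 → 38.5 for the first row. If only the proportion differs (2+2 or 8+8 of 20 at days 21+56), the planned mean is 38.5 days in both cases.

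**2. Compression of the scale.** In continuous time with a constant rate λ = ln 2/(true median) and cutoff day 56, P = 1 − exp(−56λ), and the median among normalizers is −ln(1 − P/2)/λ.

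| True median (days) | Normalized by day 56 | Median among normalizers (days) |
|---|---|---|
| 14 | 94% | 12.8 |
| 28 | 75% | 19.0 |
| 56 | 50% | 23.2 |
| 112 | 29% | 25.6 |
| 224 | 16% | 26.8 |

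A 16-fold range in speed appears as about 2-fold. With cutoff day 182, true medians of 14 and 28 days give 14.0 and 27.6, so the distortion is negligible when nearly everyone normalizes. True medians of 112 and 224 days (68% and 43% normalized) give 67 and 78.

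**3. Staged versus final analysis.** Suppose 8, 6, 3 and 3 of 20 patients first normalize at days 21, 56, 112 and 182.
- Week 8: n = 14, mean (8×21 + 6×56)/14 = 36 days.
- Week 26: n = 20, mean (8×21 + 6×56 + 3×112 + 3×182)/20 = 69.3 days.

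The same cohort appears slower only because late normalizers enter. With all 20 kept, 40% have normalized by day 21 and 70% by day 56, so the median is 56 days at both analyses.

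**4. *At* versus *by* the cutoff.** Of 20 patients, 8 normalize at day 21 (3 are raised again at day 56), 4 first normalize at day 56, and 8 never do.
- *By*: n = 12, mean (8×21 + 4×56)/12 = 32.7 days.
- *At*: n = 9, mean (5×21 + 4×56)/9 = 36.6 days.

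Both give a median of 21 days. With all 20 kept, 40% normalize by day 21 and 60% by day 56, a median of 56 days.

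**The case against.** The exclusion is explicit, pre-specified and stated twice, and the protocol gives no rule for patients who never normalize. The trial is a descriptive pilot of about 25 patients, and this is one of six additional endpoints. The plan also reports other CRP results for the whole group. Table 18 gives the share normalized at Weeks 8 and 26, and SAP 7 plans CRP values and changes from baseline at each visit for patients with baseline CRP ≥1 mg/dL, with no restriction to normalizers. SAP 9.1 requires counts, so the n in Table 19 would show how many patients contribute. With 15 eligible patients (assumed) and 10% normalizing, there are no normalizers about 21% of the time (0.9^15) and at most two about 82% of the time, so a poor response would often be obvious from n. Under a constant rate at Week 8 the normalizers-only median does separate the two cases (56 against 21 days).

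Much of this stands, and it limits the seriousness. It does not repair Table 19. Table 18 gives status at two visits rather than first normalization, CRP level by visit is not a time to normalization, and a visible n does not turn a conditional mean into a whole-group one. A cumulative percentage by visit is itself descriptive, so the decision against inferential analysis does not rule it out.

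On wording, SAP 7 describes the staged outcome as running up to the Week 8 visit date, and the event is the first qualifying draw. *By* is therefore the more natural reading, and the effect in step 4 depends on the less natural one. The days/weeks mismatch is editorial. The historical comparison has its own SAP, so harm there is only possible.

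**Conclusion.** The concern holds. As written, Table 19 and its Week 8 counterpart give a time conditional on having normalized, under a title that names the whole CRP ≥1.0 mg/dL group. The size depends on the share who normalize, which the documents do not state. Across assumed shares of 10% and 70%, the planned mean moves by 0 to 4.6 days at Week 8 and 0 to about 18 days at Week 26, while the whole-group median goes from not reached to a visit date. With 15 eligible patients and a constant rate (both assumed), the sampling SD of the Week 8 mean is about 14 days at 10% and 5.5 days at 70%, so a 4.6-day difference would not be discernible. If almost all patients normalize by the cutoff, the problem largely vanishes.

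The defect should be fixed. It is confined to one additional endpoint and does not touch the primary endpoint.

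**What to change.** In SAP 7 and 8.5.2, replace the exclusion rule along these lines:

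- Include every FAS patient with baseline CRP ≥1.0 mg/dL, using actual draw dates.
- Define the event as the first CRP ≤0.5 mg/dL on or before the analysis cutoff (*by*, not *at*). A later rise does not cancel it.
- Censor patients without an event at their last CRP draw.
- Replace Table 19 with the Kaplan-Meier cumulative percent normalized at Weeks 2-3, 8, 16 and 26, with number normalized and number at risk. Give the median as not reached where that applies. An interval-censored estimate is a reasonable alternative because CRP is drawn only at those visits.
- Use one time unit in the text and the table title.

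Patients who do not enter the extension period end at Week 8 and would be censored there, possibly for reasons related to their disease. Report how many there are and why, and read the later estimates accordingly.

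If the normalizers-only mean and median are kept, title them as applying to patients who normalized and show n/N. That label, the *by* wording and the single unit are the minimum change.

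The cost is a few lines of SAP text and one replaced table, with no new data.
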